11.5.3 Blood pressure

Systolic and diastolic blood pressure and pulse will be measured in supine position after 10 minutes of rest. Blood pressure is both an efficacy assessment and a safety assessment (Section 11.6.3) and should be registered in the vital signs form of the eCRF.

For timing of assessments refer to Table 8.1-3.

11.5.4 Questionnaires

A summary of the questionnaires and when they are scheduled to be answered is given in Table 11.5-2. Timing of the questionnaires is also outlined in the overall schedule of events (Table 8.1-3) and in the detailed schedule of events for Visit 2 to 5 (Table 8.1-4).

All questionnaires will be included in the electronic diary.

CONFIDENTIAL 59 (92)

Table 11.5-2 Summary of questionnaires

Questionnaire	CSP section	Timing
Meal pattern	11.5.4.1	Visit 2 at the clinic or at home the same day as Visit 2
		Visit 3 (± 2 days) at the clinic or at home
		Visit 4 (±2 days) at the clinic or at home
		Visit 5 at the clinic
Gastrointestinal tolerability	11.5.4.2	Visit 2 at the clinic
(GSRS)		End of Week 2 (-2 days) at home
		End of Week 4 (-2 days) at home
		Visit 3 (± 2 days) at the clinic or at home
		End of Week 8 (-2 days) at home
		Visit 4 (±2 days) at the clinic or at home
		Visit 5 at the clinic
Satiety and craving	11.5.4.3	Before breakfast, then every hour for 4 hours until lunch (total
		5 times):
		Visit 2 at the clinic and at home
		Visit 3 at the clinic and at home
		Visit 4 at the clinic and at home
		Visit 5 at the clinic and at home
Activity and sleep	11.5.4.4	Visit 2 at the clinic or at home the same day as Visit 2
		Visit 3 (± 2 days) at the clinic or at home
		Visit 4 (± 2 days) at the clinic or at home
		Visit 5 at the clinic
Health and quality of life	11.5.4.5	Visit 2 at the clinic
(RAND-36)		Visit 5 at the clinic at the same hour (± 1 h) as done on Visit 2

11.5.4.1 Meal pattern questionnaire

The questionnaire for intake of meals consists of five multiple choice questions about dietary habits, in which each question contains 4 options to select from. For each question, a score (0-3 points) is obtained.

11.5.4.2 Gastrointestinal tolerability questionnaire

The GSRS consists of 15 questions about gastrointestinal symptoms such as abdominal discomfort, heart burn, acid reflux, stomach rumbling, flatulence, constipation and diarrhoea. The questions need to be answered on the following scale: no discomfort at all, minor discomfort, mild discomfort, moderate discomfort, moderately severe discomfort, severe discomfort, very severe discomfort.

11.5.4.3 Satiety and craving questionnaire

The satiety and craving questionnaire consists of 7 questions about sense of hunger, sense of satiety and craving for certain types of food that need to be answered on a scale from 0 (not at all) to 9 (extremely much).

11.5.4.4 Activity and sleep questionnaire

The activity and sleep questionnaire consists of 2 questions about physical activity and sleep during the previous day/night.

CONFIDENTIAL 60 (92)

pharma

Clinical Study Protocol EP-002 Final version v3.0 12NOV2020

11.5.4.5 Health and quality of life (RAND-36) questionnaire

The health and quality of life questionnaire consists of 36 questions about how the patient experiences his/her own physical and mental health.

11.5.5 *Drop-out rate*

Early discontinuations should be handled as described in Section 9.8.3.

11.6 Assessments related to secondary endpoints - safety

11.6.1 Adverse events

The Principal Investigator is responsible for ensuring that all medical staff involved in the study is familiar with the content of this section and the content of CTC's standard operating procedures (SOPs) regarding emergencies.

11.6.1.1 Definition of adverse event

An AE is defined as any untoward medical occurrence in a patient administered a medicinal product and which does not necessarily have a causal relationship with this treatment. An AE can therefore be any unfavourable and unintended sign (including an abnormal laboratory finding), symptom, or disease temporally associated with the use of a medicinal product, whether or not considered related to the medicinal product.

Since GI symptoms are collected using the GSRS gastrointestinal intolerance questionnaire, the following symptoms, expected for acarbose and orlistat according to the summary of product characteristics (SmPC), will only be reported as AE in case the symptoms are of severe intensity. If severe or very severe discomfort is reported by a patient via GSRS, clinical staff will be notified and the intensity assessed by Investigator at next scheduled visit as part of normal AE assessment. If severe intensity is confirmed after Investigator judgement the GI symptom included in list below, will be reported as AE:

- Abdominal distension
- Abdominal pain
- Belching
- Bloating
- Constipation
- Diarrhoea
- Dyspepsia
- Faecal incontinence
- Flatulence
- Gastrointestinal pain
- Nausea
- Vomiting
- Oily/fatty stools
- Increased defecation
- Defecation urgency

CONFIDENTIAL 61 (92)

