6.1.2 EMP16-02 mechanism of action

EMP16-02 consists of a fixed dose combination (FDC) of orlistat and acarbose.

Orlistat is an anti-obesity drug that is administered orally during a meal and acts by preventing intestinal digestion of dietary fats and subsequent absorption of free fatty acids (FFAs) through inhibition of gastric and pancreatic lipases in the GI lumen [13,14]. Although safe, orlistat is associated with side-effects and tolerability issues that severely hamper compliance. Previous clinical trials showed that around 25% or more of the patients complain about GI side-effects including diarrhoea, oily spottings and faecal urgency [15]. Efficacy of orlistat treatment was rather modest, inducing a 10% relative body weight loss at best, while placebo induced a 6% loss of weight [16]. Orlistat in conventional form seems to have a direct effect on the stomach by increasing gastric emptying, which may lead to increased appetite

CONFIDENTIAL 23 (92)

Clinical Study Protocol EP-002 Final version v3.0 12NOV2020

[17]. The modest effect on body weight together with the tolerability issues make orlistat given in a conventional dosage form (such as Xenical®) unattractive for most obese patients.

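### The severe-only rule for reporting 15 gastrointestinal symptoms as AEs relies on the GSRS collecting them, and the protocol does not show that it does; nine are not named in its description of the questionnaire

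*Protocol*

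**What the plan says.** Section 11.6.1.1 gives both the rule and its reason. It opens: "Since GI symptoms are collected using the GSRS gastrointestinal intolerance questionnaire, the following symptoms, expected for acarbose and orlistat" according to the product information, and says that these symptoms "will only be reported as AE in case the symptoms are of severe intensity". Fifteen symptoms follow, including "Oily/fatty stools" and "Faecal incontinence". If a patient reports severe or very severe discomfort on the GSRS, staff are alerted and the investigator judges the intensity at the next scheduled visit.

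Section 11.5.4.2 is the only place that describes what the questionnaire asks: "The GSRS consists of 15 questions about gastrointestinal symptoms such as abdominal discomfort, heart burn, acid reflux, stomach rumbling, flatulence, constipation and diarrhoea". The 15 items are not reproduced.

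The protocol also says what it expects of the active ingredients. Section 6.1.2 reports that about a quarter or more of orlistat patients complain of "GI side-effects including diarrhoea, oily spottings and faecal urgency". Section 6.3 lists oily stools and increased defaecation among the side effects. Section 6.2 says that delaying orlistat release will avoid steatorrhoea. Table 7.4-1 makes both the frequency and severity of AEs and GI tolerability (by GSRS) secondary endpoints.

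**The concern.** Leaving non-severe expected effects to a questionnaire is sound only if the questionnaire asks about each of them. Here the exempt list and the questionnaire have different sources, and nothing in the protocol links one to the other.

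For an exempt symptom without an item, the AE log is told not to record a mild or moderate case, the GSRS has nowhere to score it, and the severe-discomfort alert cannot fire. The threshold is high: under the CTCAE grading in Section 11.6.1.7, severe is Grade 3, so Grade 2 events that limit instrumental daily activities are exempt too.

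At stake is the tolerability comparison. Oily stools and related effects belong to orlistat, so any under-recording would fall mainly on the two active arms, and on the effects that the formulation is meant to reduce. This is a matter of data collection, so no later analysis plan can recover events that were never recorded.

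**Working it through.** No formula applies. The check sets the exempt list beside the questionnaire description and then looks for any other record.

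**Step 1. Match the 15 exempt symptoms (Section 11.6.1.1) to the seven named topics (Section 11.5.4.2).**

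| Match | Exempt symptoms | Count |
|---|---|---|
| Named directly | constipation, diarrhoea, flatulence | 3 |
| Near equivalent named | abdominal pain and gastrointestinal pain (abdominal discomfort); dyspepsia (heart burn) | 3 |
| Not named | abdominal distension, belching, bloating, faecal incontinence, nausea, vomiting, oily/fatty stools, increased defecation, defecation urgency | 9 |

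3 + 3 + 9 = 15. Three of the seven topics are direct matches and two are the near equivalents. The other two, acid reflux and stomach rumbling, are not on the exempt list.

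**Step 2. How far the description reaches.** It names seven topics for 15 questions and offers them as examples. If each topic had one question, 15 − 7 = 8 questions would be undescribed. So the nine symptoms are not shown to be covered, and they are not shown to be uncovered.

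**Step 3. Look for another record of an unmapped, non-severe symptom.**

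- Section 11.6.1.11 collects AEs that are spontaneously reported, observed, or elicited by non-leading questions. This can pick up severe cases without a GSRS item. Non-severe cases found this way are still excluded by 11.6.1.1.
- Section 11.2 has diary questions on AEs at weeks 18 and 22, to which the same exclusion applies. Table 11.5-2 schedules no GSRS between Visit 4 (week 14) and Visit 5 (week 26).
- Section 9.8.3 requires that patients who discontinue be asked for their reasons and about AEs, and Section 17.6.6 tests GI-related drop-out. This covers only patients who leave.
- No other questionnaire in Section 11.5.4 is described as collecting gastrointestinal symptoms.

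**Step 4. What remains.** The possible gap is mild and moderate cases, in patients who stay on study, of whichever of the nine symptoms lack an item.

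**Step 5. Size.** The only rate in the protocol is the orlistat complaint rate in Section 6.1.2. Applied to one arm it gives 0.25 × 52 = 13 patients. That is an overall rate for conventional orlistat, not split by symptom or intensity, and it includes diarrhoea, which the GSRS description names. It therefore does not estimate lost cases, and the documents offer nothing better.

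**The case against.** The strongest reply is that Section 11.5.4.2 gives examples, not a full list. A symptom left out of a set of examples may still have its own question, and the document cannot settle this. That stands. A reader might infer that the GSRS has no item for oily stools, faecal incontinence or vomiting, so that these effects are recorded nowhere. The protocol does not support that. Nor does it give any ground for separating those three from the other six unnamed symptoms.

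A reader might also infer that about 13 patients per active arm would go unrecorded, or that the trial will understate orlistat effects. Neither follows: the 25% is the wrong quantity for the first, and the second depends on item content that is not given.

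It is also fair to say that handling expected, non-severe effects by questionnaire is an open and deliberate choice, that severe events keep a route to the AE log, and that patients who leave are asked why. These points limit the gap to non-severe cases in patients who remain.

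They do not remove it. A rule that switches off AE recording for listed symptoms should show that its substitute covers those symptoms, and this protocol leaves that open for nine of the 15.

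**Conclusion.** The concern holds in conditional form. The protocol exempts 15 symptoms on a premise that it supports, directly or by near equivalent, for six and leaves unshown for nine. If one or more of the nine has no GSRS item, non-severe cases of it in continuing patients would be lost for good, and effects such as oily stools could be understated in the active arms. If all nine have items, nothing is lost.

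The conclusion assumes that abdominal pain, gastrointestinal pain and dyspepsia are covered by the near-equivalent topics; if they are not, the unshown count rises to as many as 12. The number of cases at risk cannot be given from the documents. The weight-loss primary endpoint is not affected. The change should be made because it is cheap and the loss, if it occurs, cannot be repaired afterwards.

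**What to change.** In Section 11.6.1.1, limit the severe-only rule to symptoms that map to their own GSRS item. Add a short table listing the 15 GSRS items and the item for each exempt symptom. Report any listed symptom without an item as an AE at any intensity, through the existing AE questioning.

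The cost is revised wording in the protocol and the eCRF guide, plus some additional AE entries; no new questionnaire or visit is needed. If every symptom maps, the table is the only change. If some do not, the GI part of the AE tables will mix symptoms reported at any intensity with symptoms reported only when severe. Their incidences will not be comparable with each other, so the tables should carry a footnote saying which threshold applies to which symptom. Comparisons between arms within one symptom are unaffected by that mixture.

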Eligible and consenting patients will arrive at the research clinic in the morning of the first dosing day (Day 1, Visit 2) after at least 8 hours overnight fasting. A re-check of eligibility including a brief physical examination, vital signs and assessment of body weight will be conducted.

The patients will be randomised to either of two doses of EMP16-02 or placebo:

- 1. EMP16-02 120 mg O/40 mg A
- 2. EMP16-02 150 mg O/50 mg A
- 3. Placebo (identical capsules)

Blood sampling (fasting), and anthropometric measurements will be performed. Patients will receive electronic diary instructions and will be asked to fill in a satiety and craving questionnaire before breakfast (at the clinic), and then once every hour for 4 hours until before lunch (at home). A standardised breakfast will be served at the clinic. Halfway through breakfast at Visit 2, all patients will receive a placebo capsule independent of the treatment arm to which the patients have been randomised, to provide the patients with the opportunity to train on self-administering the IMP under supervision of clinic staff. The patients will also receive instructions for filling in more questionnaires regarding health and quality of life, meal pattern, activity and sleep, and gastrointestinal symptoms (gastrointestinal rating scale [GSRS], as outlined in Section 11.5.4.

The patients will be instructed to take EMP16-02 or placebo halfway through each meal, together with approximately 100-200 mL water (or other drink) on all subsequent treatment days. Once IMP has been handed out, the patients are free to leave the clinic. The first randomised IMP dose will be taken during lunch (or the next meal) at home. See Table 8.1-4 for a detailed schedule of events for Visit 2.

Patients randomised to EMP16-02 will start with a run-in period of 6 weeks during which the dose is sequentially increased. From week 7, all patients will have reached their final intended dose and a 20-week treatment and observation period will start. The run-in phase will start at a dose of 60 mg O and 20 mg A TID, which will sequentially be increased with 30 mg O/10 mg A every two weeks until the target doses of 120 mg O/40 mg A TID (for the lower dose group) and 150 mg O/50 mg A TID (for the higher dose group) are reached. The dosing regimen is summarised in Table 8.1-1.

Table 8.1-1 Increasing dosing regimen

Target dose	Week 1 and 2	Week 3 and 4	Week 5 and 6	Week 7 to 26

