	Prior and concomitant med.	11.3.5				X			

CSP=Clinical study protocol, HIV=Human immunodeficiency virus.

- 1. For detailed schedule of events, see Table 8.1-4.
- 2. At Visit 6 or after early withdrawal.
- 3. Women of child-bearing potential (WOCBP) only, urine test.
- 4. Drug tests may also be performed at additional random occasions during the study.
- 5. Full safety laboratory profile: Clinical chemistry, haematology, coagulation, urinalysis (dip stick). Fasting is not required prior to Visit 1 and Visit 6.

6. Liver enzymes: ALT, AST, ALP, GGT.

CONFIDENTIAL 39 (92)

Clinical Study Protocol EP-002 Final version v3.0 12NOV2020

- 7. Visit 5: steady-state sample pre-dose.
- 8. To be filled in by the patient during, before or after the visits, and at the end of week 2, week 4, and week 8 to follow GI symptoms during the run-in phase.
- 9. To be filled in by the patient before breakfast (at the clinic), then once every hour until lunch (at home).
- 10. To be filled in by the patient at any hour on the day of Visit 2, and at Visit 5 at approximately the same hour (± 1h) as was done at Visit 2.
- 11. IMP administration at the clinic as follows:
 - Visit 2: Placebo capsule during breakfast at the clinic, first randomised IMP dose during lunch at home.
 - Visit 3 and Visit 4: IMP dose during breakfast at the clinic.
 - Visit 5: Last IMP dose during breakfast at the clinic.
- 12. Breakfast at the clinic after weight-related assessments and blood sampling. IMP taken during breakfast.
- 13. Visit 7 applicable for patients giving their separate consent to participate in the follow-up visit.
- 14. New Informed consent required before 6 months follow-up visit. Consent may be collected at any time point prior to any study assessments at Visit 7.
- 15. Visit 7: HbA1c only
- 16. Visit 7: blood pressure only

CONFIDENTIAL 40 (92)

Clinical Study Protocol EP-002 Final version v3.0 12NOV2020

Table 8.1-4 Detailed schedule of events for Visit 2 to 5

Category	Visit	Refer to									Visit 3	3 to 5			
		CSP Section	A	t the clini	ic		At home		At	At the clinic			At home		
	Assessment		Before breakfast	00:00	01.00	02:00	03:00	04:00	Before breakfast	00:00	01.00	02:00	03:00	04:00	
Screening and	Incl./excl. criteria	11.3.2	X												
demographics assessments	Brief physical examination	11.6.2.2	X						X						
	Alcohol breath test	11.3.7	X						X						
	Pregnancy test ¹	11.3.8	X						X						
Weight-related	Weight	11.4.1	X						X						

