9.8.1 General withdrawal criteria

Patients are free to discontinue their participation in the study at any time and for whatever reason without affecting their right to an appropriate follow-up investigation or their future care. The reason for withdrawal of consent should be documented.

Patients may be discontinued from the study at any time at the discretion of the Investigator.

Reasons for discontinuation include:

- Patient withdrawal of consent
- Severe non-compliance to study protocol procedures, as judged by the Investigator. and/or Sponsor
- Patient is lost to follow-up.
- Significant AEs posing a risk for the patient, as judged by the Investigator and/or Sponsor
- Pregnancy
- Death
- Meeting of an exclusion criterion during the study, which, in the opinion of the Investigator, may pose a risk for the patient

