9.8.3 Procedures for discontinuation of a patient from the study

A patient who prematurely discontinues participation in the study will always be asked about the reason(s) for discontinuation and the presence of any AEs. If a patient withdraws consent, the Investigator must ask the patient if he/she is willing, as soon as possible, to be assessed according to the procedures scheduled for the safety follow-up visit (Visit 6). Any ongoing AEs will be followed as described in Section 11.6.1.15.

The primary reason for discontinuation/early withdrawal must be specified in the eCRF and final drug accountability must be performed.

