At Visit 3 and Visit 4 IMP will be taken at the clinic in association with breakfast. All other doses will be taken at home.

IMP will be handed out to the patients at Visit 2 (for week 1-8), Visit 3 (for week 9-14) and Visit 4 (for week 15-26).

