11.6.1.10 Reporting of action taken with study treatment

The Investigator must report the action taken with study treatment using the definitions below and record it on the AE Log of the eCRF:

Dose increased

Dose not changed

Dose rate reduced

Dose reduced

Drug interrupted

Drug withdrawn

Not applicable

Unknown

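### A severe GSRS report during run-in requires no Investigator assessment until Visit 3, after up to three further dose steps

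*Protocol*

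**What the plan says.** Section 11.6.1.1 makes a set of expected GI symptoms reportable as adverse events only if they are severe. If a patient scores severe or very severe discomfort on the GSRS, "clinical staff will be notified and the intensity assessed by Investigator at next scheduled visit as part of normal AE assessment". The symptom becomes an AE once the Investigator has confirmed severe intensity.

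The surrounding schedule is as follows.

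- **Titration (8.1, Table 8.1-1).** The starting dose is 60 mg orlistat/20 mg acarbose, which will "sequentially be increased with 30 mg O/10 mg A every two weeks until the target doses" are reached. It is a fixed calendar; no GSRS result holds or changes it.
- **GSRS (Table 8.1-3 footnote 8; Table 11.5-2).** Besides the visits, it is completed "at the end of week 2, week 4, and week 8 to follow GI symptoms during the run-in phase". The first of these is timed "End of Week 2 (-2 days) at home", and week 4 has the same window.
- **Visits (Table 8.1-3).** After Visit 2 on Day 1, the next is Visit 3 on Day 46 ±3.
- **Supply (10.5).** "IMP will be handed out to the patients at Visit 2 (for week 1-8"), so all run-in capsules are at home from Day 1.
- **Other contact.** The diary asks about AEs only at weeks 18 and 22 (11.2). Under 9.8.1, "Patients may be discontinued from the study at any time at the discretion of the Investigator". Under 9.8.3, a patient who discontinues "will always be asked about the reason(s) for discontinuation and the presence of any AEs".

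**The concern.** The run-in exists because GI intolerance is milder when the dose is raised slowly (8.3), and the extra GSRS assessments are there to follow symptoms over that period. The week-2 and week-4 questionnaires fall just before a dose step, and the notification reaches staff in time to act. Yet the rule ties the alert to no action before that step. The only assessment it requires comes when the low arm has already been at target since Day 29 and the high arm is at or past its last step.

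Two things are at stake.

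- **Safety.** A patient with severe discomfort at the lowest dose can go through all remaining steps without any required medical contact.
- **AE data.** For the listed symptoms, AE status depends on the Investigator's grading. For patients who stay on treatment, that grading is made 2 to 5 weeks later, from recall and at a different dose.

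**Working it through.** **Calendar.** Week *w* covers Day 7(*w*−1)+1 to Day 7*w*. Week 7 is then Days 43-49, which matches the protocol's Day 46 ±3 for Visit 3. The same rule reproduces Visit 4 (week 14, Days 92-98 = Day 95 ±3) and Visit 5 (week 26, Days 176-182 = Day 179 ±3).

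**Dates**

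- GSRS at end of week 2 (−2 days): Days 12-14. At end of week 4 (−2 days): Days 26-28.
- Dose steps: 90/30 from Day 15 and 120/40 from Day 29 in both active arms; 150/50 from Day 43 in the high arm.

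**Wait from alert to Visit 3**

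- Week-2 alert: 43 − 14 = 29 days to 49 − 12 = 37 days.
- Week-4 alert: 43 − 28 = 15 days to 49 − 26 = 23 days.

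**Doses above the level in use at the alert**, three per day, up to breakfast at Visit 3, assuming full compliance on active drug:

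| Alert | Visit 3 on Day 43 | Day 46 | Day 49 |
|---|---|---|---|
| Week 2 (above 60/20, from Day 15) | (43−15)×3 = 84 | (46−15)×3 = 93 | (49−15)×3 = 102 |
| Week 4 (above 90/30, from Day 29) | (43−29)×3 = 42 | (46−29)×3 = 51 | (49−29)×3 = 60 |

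**Split of the 84-102 doses after a week-2 alert**

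- Days 15-28: 14×3 = 42 doses at 90/60 = 1.5 times the starting dose.
- Days 29-42: 14×3 = 42 doses at 120/60 = 2.0 times.
- Day 43 to Visit 3: 0 to (49−43)×3 = 18 doses, at 2.0 times in the low arm and 150/60 = 2.5 times in the high arm.

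**Time available for a call before the next step**

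- Week 2: 15 − 14 = 1 day to 15 − 12 = 3 days.
- Week 4: 29 − 28 = 1 day to 29 − 26 = 3 days.

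**Week-8 alert.** Days 54-56 to Visit 4 (Days 92-98): 92 − 56 = 36 to 98 − 54 = 44 days. Titration is complete by then, so only the delay matters.

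**Workload.** The protocol gives no alert rate. Assuming 5-25% of 156 patients trigger one alert each: 0.05×156 = 7.8, about 8 calls, to 0.25×156 = 39 calls.

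**The case against.** The strongest reply is that 11.6.1.1 defines adverse events. Its sentence fixes when intensity is graded for classification and does not tell staff to wait. They are notified at once, the Investigator can stop a patient at any time (9.8.1), patients carry the Investigator's phone number (14.4) and can report AEs spontaneously (11.6.1.11), and SAEs have a 24-hour route (11.6.1.13). The symptoms are expected and are described as transient (6.3), and 120/40 was well tolerated in the previous phase IIa study (8.3). A GSRS score is a patient rating, not a CTCAE grade, and it is stored when given (16.3). One third of patients (52 of 156) are on placebo, so their dose does not rise.

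Much of this is correct, but it does not remove the point.

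- The discretionary routes allow earlier contact; none requires it. The SAE route does not cover severe but non-serious GI symptoms.
- Section 6.3 says the side effects resolve when the drug is stopped. Here dosing continues and increases. The earlier study's highest orlistat dose was 120 mg, so it does not cover 150/50.
- The stored GSRS answer helps, but it cannot replace CTCAE grading (11.6.1.7), which rests on function and need for intervention.
- The placebo share and the 1.5/2.0/2.5 split do qualify the size. The 2.5-fold level applies to the high arm only, for at most 18 doses before Visit 3.

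**Conclusion.** The concern holds and should be fixed. The dates follow directly from the schedule, and nothing in the protocol requires an Investigator to assess a week-2 or week-4 alert before Visit 3. The wait is 29-37 days after a week-2 alert and 15-23 days after a week-4 alert. The dose counts assume full compliance on active drug without self-discontinuation. How many patients would be affected is unknown, because the protocol gives no alert rate.

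The consequence is limited to patient safety during titration and the quality of severe GI AE grading. The GSRS endpoint is recorded at the time and is unaffected. No bias in the between-arm tolerability comparison is claimed, and sample size, power and the primary analysis are untouched.

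**What to change.** In 11.6.1.1, replace the reference to the next scheduled visit with a prompt telephone assessment by the Investigator: before the next run-in dose step where feasible, otherwise within 3 days of the alert. At the call, record intensity and onset date (the dose at onset then follows from Table 8.1-1), and confirm at the next visit. State that the Investigator may interrupt or stop IMP on the basis of the call.

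The change does not gate titration. A Day-14 alert might be called only on Day 17, after the Day-15 step, but by the start of that day the patient would have taken (17−15)×3 = 6 doses at the higher level, compared with 84-102 under the present rule. The 3-day limit also covers week-8 alerts.

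The cost is one sentence in the protocol and a site instruction. The staff notification already exists, and "Drug interrupted" and withdrawal of drug are already action-taken options in 11.6.1.10, so no new eCRF category, capsule strength or packaging is needed. The downside is one call per alert, about 8-39 in all under the assumed rate, in a window of 1-3 days that may include a weekend.
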